Respiratory manifestations include respiratory muscle weakness, obstructive sleep apnoea, mucus plugging and respiratory failure (Birnkrant 2018). After age 10 to 14, patients gradually begin to lose respiratory muscle function based on pulmonary function tests (PFTs) such as forced vital capacity (FVC). The median loss in FVC (% predicted) is estimated to be 8.0% per year (Phillips 2001; Tangsrud 2001).

Dystrophin deficiency in the heart causes cardiomyopathies which are later responsible for cardiac complications. With the progression of the disease, the myocardium fails to meet physiological demands and clinical manifestations of heart failure occur such as fatigue, weight loss, vomiting, abdominal pain, sleep disturbance and inability to operate daily activities (Birnkrant 2018). Because of improvements in respiratory care, cardiac dysfunction is now a leading cause of morbidity and mortality in DMD patients (Schram 2013). Progressive myocardial fibrosis, as detected by late gadolinium enhancement (LGE), is strongly correlated with the left ventricular ejection fraction (LVEF) decline in Duchenne muscular dystrophy patients. Longer steroid treatment duration is associated with a lower age-related increase in myocardial fibrosis burden (Tandon 2015).

Boys treated for DMD have low-trauma extremity fractures as a result of osteoporosis, and 30% may develop symptomatic vertebral and leg fractures due to bone fragility. Osteoporosis is a side effect of glucocorticoid therapy. Those bone manifestations can lead to chronic back pain, spine deformity, bone fractures, scoliosis and premature or permanent loss of ambulation (Birnkrant 2018). As dystrophin is also expressed in the central nervous system (CNS), other clinical manifestations of DMD patients are neuropsychological problems, and neurobehavioral abnormalities (Annexstad 2014; Tsuda 2018; Zhou 2010). Endocrine disturbances also occur in part of adolescents with DMD. Those hormonal disorders provoke a delay in the age of puberty and short stature problems (Annexstad 2014; Leung 2011; Zhou 2010).

Maximal life-expectancy of DMD patients is currently estimated at 30–40 years of age (Walter 2017). Corticosteroid treatment and higher standards of medical care such as artificial respirators have considerably improved survival within the last two decades (Birnkrant 2018; Bushby 2010; Falzarano 2015; van Westering 2015; Wu 2014).

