2.6.7. Forced Expiratory Volume at 1 Second (FEV1)

FEV1 assesses airway function and is the standard global assessment in both clinical and research studies of asthma, chronic obstructive pulmonary disease, and cystic fibrosis. FEV1 is understood to correlate closely with FVC, with the advantage of requiring less prolonged effort (1 second). (Finder, 2017). Data from the placebo group, in the DELOS study (Buyse, 2015) have shown that yearly rates of ppFEV1 decline were -10.2% [SD 2.0] (Meier, 2017). Cardiac fibrosis score/ Late gadolinium enhancement (LGE)

Late Gadolinium Enhancement (LGE) is a strong marker for the progression of left ventricular systolic dysfunction in DMD patients. Improvements in the cardiac function observed above are further supported by the reduction in cardiac fibrosis assessed by LGE, which is a strong marker for the progression of left ventricular systolic dysfunction in DMD patients.

Additionally, cardiac fibrosis, assessed by mass of late gadolinium enhancement (MLGE) showed a correlation between improvement in LVEF% and reduction in cardiac fibrosis, mentioned in Tandon, et al 2015 (Tandon, 2015).

2.6.8. Fibrosis and FAT assessment of the Upper Arm (Biceps brachii) assessed by MRI

In the recent years, several longitudinal studies have reported the potential value of MRI as a biomarker to assess disease progression and treatment effect in DMD. MRI biomarkers provide the advantage of studying different muscle groups in both lower and upper limbs, enabling assessment of disease progression in not only ambulant, but also non-ambulant patients incapable of performing physical tests, in addition to being an objective measure not influenced by patient's motivation during functional tests (Szigyarto 2018).

T2-mapping can help determine the level of inflammation, oedema, and fat infiltration present in the affected muscle (Magrath 2018).

Overall, the results from the completed phase 2 main study in non-ambulatory DMD subjects show that pamrevlumab may have a beneficial effect on several clinically meaningful parameters affecting the DMD population. Pamrevlumab, as an antifibrotic agent, has shown the potential to slow disease progression in patients with DMD. That, in addition to being well tolerated in pediatric patients, is considered of significant clinical benefit. Therefore, the risk-

benefit ratio remains favorable. For more information please reference the current Investigator's Brochure.

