8.3.4.2. Analyses of Secondary Endpoints

Changes in ppFVC and ppPEF from Baseline to Week 52

The Change from baseline to Week 52 in ppFVC will be analyzed using a random coefficient model with treatment, visit, visit-by-treatment interaction, and baseline ppFVC as fixed effects; the intercept and linear slope of visit as random effects. The analysis will be based on observed data from subjects in the ITT population.

The Change from baseline to Week 52 in ppPEF will be analyzed using a random coefficient model with treatment, visit, visit-by-treatment interaction, and baseline ppPEF as fixed effects; the intercept and linear slope of visit as random effects. The analysis will be based on observed data from subjects in the ITT population.

Change in the Grip Strength of the Hands from baseline to Week 52, assessed by Hand Held Myometry (HHM)

The Change from baseline to Week 52 in grip strength of the hands will be analyzed using a random coefficient model with treatment, visit, visit-by-treatment interaction, and baseline value as fixed effects; the intercept and linear slope of visit as random effects. The analysis will be based on observed data from subjects in the ITT population.

Change in Left Ventricular Ejection Fraction percentage (LVEF %) from Baseline to Week 52, Assessed by MRI.

Summary of Listing and the analyses of the change from baseline to week 52 in LVEF (%) assessed by MRI will be conducted in the ITT population.

The change from baseline to Week 52 in left ventricular ejection fraction percentage (LVEF%), as assessed by MRI will be analyzed using a random coefficient model with treatment, visit, visit-by-treatment interaction, and baseline value as fixed effects; the intercept and linear slope of visit as random effects.

As an exploratory endpoint, the dichotomous responder (proportion of patients with change from baseline in LVEF% ≥ 0 at Week 52) will be summarized and analyzed. The logistic regression model will be used to compare the proportion of subjects with change from baseline in LVEF% ≥ 0 . The model will include treatment and baseline LVEF%.

For other secondary endpoints, MMRM model will be used in continuous variables; logistic regression model in binary variables; Cox regression model in time-to-event variables. The analysis models will include appropriate baseline factors. Other methods will be applied as appropriate.

Detailed analyses of all secondary endpoints will be clearly outlined in the SAP.

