In addition, dichotomous responder analysis (proportion of patients with change from baseline in GCS score ≥ 0 at Week 52) will be summarized and analyzed. The logistic regression model will be used to compare the proportion of subjects with change from baseline in GCS score ≥ 0 . The model will include treatment and baseline cardiac fibrosis score.

Changes in Fibrosis Score of the Biceps Brachii from Baseline to Week 52, Assessed by MRI

Summary of the listings and analyses of upper arm (bicep) muscle fibrosis assessed by MRI, will be summarized based on ITT population;

The change from baseline to Week 52 in fibrosis score of the biceps brachii muscle assessed by MRI will be analyzed using the Mixed Model for Repeated Measure (MMRM) with treatment, visit, treatment-visit interaction, and baseline endpoint value as fixed effects, with an unstructured variance - covariance matrix

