**Table 1: Testing Sequence of Primary and Secondary Endpoints**

Testing Sequence	Endpoint
1 (primary endpoint)	Change in the total score of Performance of Upper Limb [(PUL) version 2.0], from baseline to Week 52.
2	Change in percent predicted Forced Vital Capacity (ppFVC) from baseline to Week 52, assessed by spirometry.
3	Change in the total score of Mid-level of PUL from baseline to Week 52
4	Change in the grip strength of the hands from baseline to Week 52, assessed by Hand-Held Myometry (HHM).
5	Change in Left Ventricular Ejection Fraction percentage (LVEF %) from baseline to Week 52, assessed by MRI.

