#### 6.6.2.3.2. Analysis Variables

##### 6.6.2.3.2.1. Change in Left Ventricular Ejection Fraction Percentage (LVEF %) from Baseline to Week 52, Assessed by MRI

##### 6.6.2.3.3. Population Summary for Treatment Comparison

The change in the LVEF% from baseline to Week 52 will be analyzed using an ANCOVA model, which contains terms for treatment, baseline LVEF measurements. The LSMean and corresponding SE for the change from baseline in LVEF at Week 52 will be estimated.

Sample SAS code:

```
/* excluding baseline visit */
```

```
PROC MIXED DATA=ANCOVA METHOD=ML;  
  CLASS TRTP;  
  MODEL CHG = TRTP BASE / DDFM = KR;  
  LSMEANS TRTP /PDIFF CL;  
RUN;
```

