**6.6.3.6.2. Changes in Cardiac Fibrosis Score from Baseline to Week 52, Assessed by Late Gadolinium Enhancement (LGE).**

Summary of the listings and analyses of changes in cardiac fibrosis (LGE) will be based on the ITT population.

The change from baseline to Week 52 in cardiac fibrosis score assessed by MRI and Mass of Late Gadolinium Enhancement (Scar Mass) between two treatment arms, will be compared by ANCOVA. The ANCOVA model will contain terms for treatment and baseline measurements.

In addition, dichotomous responder analysis (proportion of patients with change from baseline in cardiac fibrosis score  $\geq 0$  at Week 52) will be summarized and analyzed. The logistic regression model will be used to compare the proportion of subjects with change from baseline in cardiac fibrosis  $\geq 0$ . The model will include treatment and baseline cardiac fibrosis score.

**6.6.3.7. Change in Myocardial Circumferential Strain [Global Circumferential Strain (GCS)%] percentage from Baseline to Week 52, Assessed by cardiac MRI.**

Summary of the listings and analyses of annual changes from baseline for the Global Myocardial Circumferential Strain (GCS) will be summarized for subjects in the ITT population,

The change from baseline to Week 52 in GCS score between two treatment arms will be compared by ANCOVA. The ANCOVA model will contain terms for treatment and baseline measurements.

In addition, dichotomous responder analysis (proportion of patients with change from baseline in GCS score  $\geq 0$  at Week 52) will be summarized and analyzed. The logistic regression model will

be used to compare the proportion of subjects with change from baseline in GCS score  $\geq 0$ . The model will include treatment and baseline cardiac fibrosis score.

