- Expert guidance from key opinion leaders for PUL 2.0 [REDACTED] strongly support the approach of removal of patients with PUL 2.0 entry scores of 1 because these patients do not demonstrate significant decline over a 1-year period and therefore impact meaningful opportunity to demonstrate efficacy.

- Based on changes in the external environment for DMD studies, the Sponsor conducted an analysis of current trials from clinicaltrials.gov and concluded that other clinical trials in the non-ambulatory DMD patient population using the PUL 2.0 as a primary endpoint measure have excluded patients with a PUL 2.0 entry score of 1 at baseline. For example, Capricor Inc./NCT05126758 A Phase 3, Randomized, Double-Blind, Placebo-Controlled Trial Evaluating the Efficacy and Safety of Human Allogeneic Cardiosphere-Derived Cells for the Treatment of Duchenne Muscular Dystrophy A Study of CAP-1002 in Ambulatory and Non-Ambulatory Patients with Duchenne Muscular Dystrophy (HOPE-3).
- Non-ambulatory DMD patients have limited treatment options and have been excluded from clinical trials in emerging treatment classes. Modification of the analysis will result in benefit to non-ambulatory patients as well as increased treatment options.
- The Sponsor has determined that removal of patients with a baseline PUL 2.0 entry score of 1.0 will result in approximately 15 patients removed from the ITT population. The sample size and power calculations are based on the assumptions described in the protocol, and with 15 fewer subjects out of 97 dosed subjects, the trial will have 87% power with 82 subjects in the mITT population.
- Sample size calculation was updated per the latest literature publications and study enrollment. The testing sequence of secondary endpoints was changed from the protocol.
- Changed the analysis method for subscores of regional dimensions (High-level (Shoulder), Distal-level (Wrist and Hand)) of PUL from MMRM to RCM, the same one used in the primary analysis.
- The analysis methods for change from baseline at week 52 in LVEF, Fibrosis Score of the Biceps Brachii, Cardiac Fibrosis Score, Myocardial Circumferential Strain [Global Circumferential Strain (GCS)%] percentage are changed from MMRM to ANCOVA respectively, because there are only two assessments performed during the study for these exploratory endpoints – one at baseline and the other at week 52 and it is not suitable for mixed models of repeated measures.

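### The SAP counts unchanged or increased cardiac fibrosis as response (change ≥ 0, against the protocol's ≤ 0 definition), and its LVEF sample code uses METHOD=ML, which makes an alpha-controlled test slightly too liberal

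*SAP*

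**What the plan says.** **Cardiac fibrosis responder.** SAP 6.6.3.6.2 adds to the continuous ANCOVA a "dichotomous responder analysis (proportion of patients with change from baseline in cardiac fibrosis score" ≥ 0 at Week 52). Its next sentence fits a logistic regression to the same ≥ 0 outcome. Protocol 8.3.5 uses the same words but sets the cut at ≤ 0, and then names ≥ 0 in its own logistic sentence.

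**Direction of benefit.** Protocol 2.2 says: "Progressive myocardial fibrosis, as detected by late gadolinium enhancement (LGE), is strongly correlated with the left ventricular ejection fraction (LVEF) decline". Protocol 2.6.7 says that LGE mass "showed a correlation between improvement in LVEF% and reduction in cardiac fibrosis". A ≥ 0 cut does appear where it is favourable, for ejection fraction: Protocol 8.3.4.2 defines "the dichotomous responder (proportion of patients with change from baseline in LVEF"% ≥ 0.

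**What SAP Section 7 records.** The methods for LVEF, biceps fibrosis, cardiac fibrosis and GCS "are changed from MMRM to ANCOVA respectively, because there are only two assessments performed during the study". The responder cut is not mentioned.

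**LVEF test.** Step 5 of SAP Table 1 is "Change in Left Ventricular Ejection Fraction percentage (LVEF %) from baseline to Week 52, assessed by MRI", and SAP 6.6 tests each step at 0.05. The prose of SAP 6.6.2.3.3 asks only for an ANCOVA with treatment and baseline. Its sample code opens with "PROC MIXED DATA=ANCOVA METHOD=ML" and uses DDFM=KR.

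**GCS responder model.** In Protocol 8.3.5 and SAP 6.6.3.7 the logistic model for GCS change ≥ 0 has this specification: "The model will include treatment and baseline cardiac fibrosis score". Baseline GCS is not in it.

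**The concern.** The fibrosis cut points the wrong way. If the drug reduces fibrosis, a programmer who follows the SAP will produce a table in which pamrevlumab has the lower responder rate. Turning the table upside down afterwards does not recover the protocol's definition. Subjects with zero change are responders under both cuts, so the inverse of the SAP odds ratio belongs to a < 0 definition, not to ≤ 0. Someone would then have to choose the definition with the results in hand.

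The LVEF point concerns type I error in a test that can support a confirmatory claim. Maximum likelihood divides the residual sum of squares by n, whereas REML and ordinary ANCOVA divide by n − 3. The standard error is then too small and the test rejects more often than 5%.

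The GCS covariate is a minor matter. It looks carried over from the fibrosis paragraph. It does not invalidate the comparison, but it adjusts for the wrong baseline. The documents give no sign convention for GCS, so a reader cannot tell whether ≥ 0 is the good or the bad direction.

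**Working it through.** **Fibrosis: the texts side by side**

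| Place | Definition of responder | Outcome in logistic model |
|---|---|---|
| Protocol 8.3.5 | change ≤ 0 | change ≥ 0 |
| SAP 6.6.3.6.2 | change ≥ 0 | change ≥ 0 |

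Only the protocol's definition agrees with the direction of benefit in Protocol 2.2 and 2.6.7.

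**Fibrosis: size.** The documents give neither improvement rates nor the share of subjects with exactly zero change, so both are assumed. Let z be the zero-change share and i the proportion improving among subjects with non-zero change, with i = 0.40 on drug and 0.25 on placebo. Then

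- P(change ≤ 0) = i(1 − z) + z
- P(change ≥ 0) = (1 − i)(1 − z) + z

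For z = 0.2:

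- ≤ 0: drug 0.40 × 0.8 + 0.2 = 0.52; placebo 0.25 × 0.8 + 0.2 = 0.40; OR = (0.52/0.48)/(0.40/0.60) = 1.62
- ≥ 0: drug 0.60 × 0.8 + 0.2 = 0.68; placebo 0.75 × 0.8 + 0.2 = 0.80; OR = (0.68/0.32)/(0.80/0.20) = 0.53

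| z | ≤ 0, drug v placebo | OR | ≥ 0, drug v placebo | OR | inverse of ≥ 0 OR |
|---|---|---|---|---|---|
| 0 | 40% v 25% | 2.00 | 60% v 75% | 0.50 | 2.00 |
| 0.2 | 52% v 40% | 1.62 | 68% v 80% | 0.53 | 1.88 |
| 0.4 | 64% v 55% | 1.45 | 76% v 85% | 0.56 | 1.79 |

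The direction is reversed in every row. The inverse matches the protocol's definition only when no change is exactly zero.

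**LVEF: inputs.** The analysis set is the mITT, with 82 subjects (SAP Section 7: 97 dosed less about 15). The model has an intercept, treatment and baseline, so three mean parameters, and no RANDOM or REPEATED statement. Nominal alpha is 0.05 two-sided (SAP 6.6).

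The plan's own figures for these sample sizes reproduce. With a difference of 2.0 and SD of 2.9, the exact two-sided t-test has 90.5% power at 92 subjects (stated 90%) and 87.0% at 82 (stated 87%). The plan gives no figure for the actual alpha of the LVEF test.

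**LVEF: calculation.**

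1. SE ratio, ML to REML = √((n − 3)/n). At n = 82 this is √(79/82) = 0.9815, so the SE is 1.8% too small.
2. Kenward-Roger does not repair this. With one residual variance as the only covariance parameter, its covariance adjustment is zero.
3. True alpha = 2 × P(t with n − 3 df > t(0.975, df) × ratio), computed with the critical value on n − 3 df and on n df.

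| Subjects with both MRIs | SE ratio | Alpha, df = n − 3 | Alpha, df = n |
|---|---|---|---|
| 60 (assumed) | 0.9747 | 5.59% | 5.61% |
| 70 (assumed) | 0.9783 | 5.50% | 5.52% |
| 82 (mITT) | 0.9815 | 5.43% | 5.44% |
| 97 (all dosed) | 0.9844 | 5.36% | 5.37% |

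A simulation of 200,000 null trials at 41 per arm agrees. With the critical value on 79 df, ML rejects in 5.39% and REML in 4.96%.

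The SAP's other PROC MIXED samples (Sections 6.6.1.1.5, 6.6.1.2.1.5, 6.6.1.2.3.5 and 6.6.2.2.3) set no METHOD and so use the REML default. The LVEF code is the exception, and the prose gives no reason for it.

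**The case against.** The strongest reply is that little depends on either point. The fibrosis responder table is exploratory, lies outside Table 1, and supplements an ANCOVA on the continuous change that keeps its direction. A table that prints its cut lets a careful reader see which way the proportion runs. The protocol is not clean either, since the SAP's model matches the protocol's logistic sentence. This is an inconsistency in the protocol that the SAP resolved the wrong way.

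On LVEF, the option sits in code labelled as a sample, beside other samples with unfilled placeholders (a literal COVARIATES term, SHIFT=-##), and the prose asks only for an ANCOVA. Even run verbatim, the excess is about 0.4 percentage points, in the last step of the sequence, reached only after four successes. The composite z-score uses a permutation p-value, where the scaling largely cancels if the same code is rerun.

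All of this limits the size, and it stands to that extent. The gaps between odds ratios also depend on assumed rates. It does not make either rule right. The SAP definition still labels worsening as response, nothing in Section 7 suggests this was deliberate, and the continuous analysis does not correct the responder table. Sample code is what a programmer is likely to start from, and nothing in the text overrides the option.

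**Conclusion.** The concern holds, and the points should be corrected before unblinding.

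- **Fibrosis responder:** the SAP rule is reversed against the documents' own direction of benefit. A true reduction in fibrosis would appear as a lower responder rate on drug. The reversal itself needs no assumption; the percentages and odds ratios rest on the assumed improvement rates and zero-change shares. The consequence is confined to an exploratory analysis.
- **LVEF:** run as written, the two-sided test has an alpha of about 5.4% at 82 subjects and 5.5% at an assumed 70. This rests on the sample code being used verbatim and on the number of subjects with both MRIs. It can affect a confirmatory claim only if steps 1 to 4 succeed. The primary analysis is not affected.
- **GCS:** the wrong baseline covariate in a supplementary model is a minor error. The direction of its cut cannot be judged from the documents.

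**What to change.** 1. In SAP 6.6.3.6.2 use change ≤ 0 in both the definition and the logistic sentence. Correct the logistic sentence of Protocol 8.3.5 to match, or record the correction in SAP Section 7.
2. Delete METHOD=ML from the sample code in SAP 6.6.2.3.3 so that REML applies.
3. In SAP 6.6.3.7 and Protocol 8.3.5 use baseline GCS as the covariate in the GCS logistic model, and state the GCS sign convention so that the ≥ 0 cut can be interpreted.

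The cost is a few words and one code option. Protocol 8.4 leaves detailed models and definitions to the SAP, and SAP Section 1 provides for an SAP amendment, so the SAP corrections need not wait for a protocol amendment. The LVEF confidence interval becomes about 1.9% wider at 82 subjects (1/0.9815 = 1.019) and 2.2% wider at an assumed 70 (1/0.9783 = 1.022).

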4.2. Subject Exclusion Criteria

Subjects will be ineligible for and excluded from this trial if any of the following apply:

General criteria:

1. Previous exposure to pamrevlumab
2. BMI ≥ 40 kg/m² or weight >117 kg
3. History of:
 - a. allergic or anaphylactic reaction to human, humanized, chimeric or murine monoclonal antibodies
 - b. hypersensitivity to study drug or any component of study drug
 - c. hypersensitivity reaction to Gadolinium-based Contrast Agents (GBCA) required for MRI acquisition
4. Exposure to any investigational drug (for DMD or not), in the 30 days prior to screening initiation or use of approved DMD therapies (e.g., eteplirsen (exondys 51), ataluren, golodirsen (vyondys 53), casimersen (amondys 45)) within 5 half-lives of screening, whichever is longer, with the exception of the systemic corticosteroids, including deflazacort

Cardiac, Renal, and Pulmonary assessment:

5. Severe uncontrolled heart failure (NYHA Classes III-IV), or renal dysfunction, including any of the following:
 - a. Need for intravenous diuretics or inotropic support within 8 weeks prior to screening
 - b. Hospitalization for a heart failure exacerbation or arrhythmia within 8 weeks prior to screening
 - c. Patients with glomerular filtration rate (GFR) of less than 30 mL/min/1.73m² or with other evidence of acute kidney injury as determined by investigator
6. Arrhythmia requiring anti-arrhythmic therapy
7. Requires ≥ 16 hours continuous ventilation

8. Hospitalization due to respiratory failure within the 8 weeks prior to screening
9. Poorly controlled asthma or underlying lung disease such as bronchitis, bronchiectasis, emphysema, recurrent pneumonia that in the opinion of the investigator might impact respiratory function

Clinical judgments:

10. The Investigator judges that the subject will be unable to fully participate in the study and complete it for any reason, including inability to comply with study procedures and treatment, or any other relevant medical or psychiatric conditions which could confound efficacy assessment and/or safety assessment.

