**Fibrosis/MRI assessments:**

- Changes in fibrosis score of the biceps brachii, from baseline to Week 52, assessed by MRI
- Changes in cardiac fibrosis score from baseline to Week 52, assessed by Late Gadolinium Enhancement (LGE)
- Change in Myocardial Circumferential Strain [Global Circumferential Strain (GCS)] percentage from baseline to Week 52, assessed by cardiac MRI

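### The GCS responder model adjusts for baseline cardiac fibrosis and omits baseline GCS, unlike every comparable cardiac analysis in the plan; probably carried-over wording in an exploratory analysis

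*SAP*

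**What the plan says.** SAP 6.6.3.7 plans two analyses of GCS in the ITT population.

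- **Continuous:** "The change from baseline to Week 52 in GCS score between two treatment arms will be compared by ANCOVA". The covariates follow: "The ANCOVA model will contain terms for treatment and baseline measurements". I read the baseline here as baseline GCS. Protocol 8.3.5 supports that reading, because its mixed model for GCS uses the endpoint's own baseline value.
- **Responder:** a "dichotomous responder analysis (proportion of patients with change from baseline in GCS score" of zero or more at Week 52, fitted by logistic regression. For this model the SAP states: "The model will include treatment and baseline cardiac fibrosis score". Protocol 8.3.5 says the same, so the two documents agree with each other.

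The same sentence closes SAP 6.6.3.6.2, where the responder is defined on cardiac fibrosis and the covariate fits. For the LVEF responder, Protocol 8.3.4.2 states: "The model will include treatment and baseline LVEF" (as a percentage).

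The two measures are described differently in SAP 4.4. Fibrosis is listed as "Changes in cardiac fibrosis score from baseline to Week 52, assessed by Late Gadolinium Enhancement (LGE"), and GCS as a change in "percentage from baseline to Week 52, assessed by cardiac MRI".

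**The concern.** The outcome is the sign of Week 52 GCS minus baseline GCS. Baseline GCS is therefore part of the outcome and the natural covariate. Using another endpoint's baseline has three possible costs:

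- Some power is given up.
- The responder and continuous analyses of one endpoint condition on different baselines, so they are harder to read together.
- The model needs a late-gadolinium score that the outcome itself may not need.

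SAP section 7 explains why the continuous GCS analysis moved from a mixed model to ANCOVA but does not mention this covariate.

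**Working it through.** **1. The plan's own pattern.** No sample size, power or rate is stated for this model, so there is no plan figure to reproduce. The texts compare as follows.

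| Analysis | Where | Baseline covariate |
|---|---|---|
| LVEF responder | Protocol 8.3.4.2 | LVEF |
| Cardiac fibrosis responder | Protocol 8.3.5, SAP 6.6.3.6.2 | cardiac fibrosis |
| GCS, continuous | Protocol 8.3.5, SAP 6.6.3.7 | GCS (own baseline) |
| GCS responder | Protocol 8.3.5, SAP 6.6.3.7 | cardiac fibrosis |

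Only the last row borrows another endpoint's baseline.

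**2. Why baseline GCS is related to the outcome.** Let r be the correlation of baseline and Week 52 GCS, with equal variances (assumptions; neither is in the documents). Then Var(change) = 2σ²(1 − r) and Cov(baseline, change) = −σ²(1 − r), so corr(baseline, change) = −√((1 − r)/2).

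- r = 0.5: −0.50, squared 25%
- r = 0.7: −0.39, squared 15%
- r = 0.9: −0.22, squared 5%

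These squares describe the continuous change score. They do not measure the loss in the logistic model, so that was simulated.

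**3. Effect on the logistic model.** Inputs: N = 92, 1:1 (SAP 3.3). All of the following are assumed: a treatment shift of 0.6 SD of change; no average change on placebo, so half of placebo boys respond; correlation of fibrosis with baseline GCS of 0, 0.3 or 0.5; 3,000 runs per setting. Ranges are over the three fibrosis correlations.

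| r | Power, baseline GCS | Power, baseline fibrosis | Loss (points) | Power, fibrosis with 10% of scores missing |
|---|---|---|---|---|
| 0.5 | 66.6–67.6% | 60.1–61.2% | 5.4–6.7 | 56.0–56.8% |
| 0.7 | 64.9–65.7% | 59.8–62.1% | 3.6–5.1 | 56.7–57.2% |
| 0.9 | 61.4–62.9% | 59.5–61.1% | 1.8–2.0 | 53.6–56.5% |

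A further run on assumed inputs of the same kind put the loss at about 1 to 6 points, so I take 1 to 7 as the range.

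**Hand check of the fibrosis column.** If fibrosis is unrelated to GCS, the model is close to an unadjusted comparison. The treated response is Φ(0.6) = 0.726 against 0.5 on placebo.

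- Log odds ratio: ln(0.726/0.274) = 0.97.
- SE: √(1/(46 × 0.25) + 1/(46 × 0.726 × 0.274)) = √(0.087 + 0.109) = 0.44.
- Power: about Φ(0.97/0.44 − 1.96) = Φ(0.24), or about 60%, which agrees with the table.

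**4. Validity.** With no treatment effect, and a fibrosis correlation of 0.3, rejection rates at r = 0.5 and r = 0.9 were 4.7% and 5.0% with baseline GCS. They were 5.2% and 4.9% with fibrosis, and 4.4% and 4.9% with fibrosis and 10% missing.

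**5. Missing fibrosis scores.** An ordinary logistic fit uses only subjects with every covariate present. SAP 5.3.5 leaves missing-data handling to the individual endpoints, and 6.6.3.7 gives no rule for a missing covariate. Each boy with GCS but no baseline fibrosis score would cost 1/92 = 1.1% of the planned sample. If 10% lacked a score (assumption), the further loss is 3.1 to 5.9 points. The documents give no count, and it may be zero. Baseline GCS adds no such loss, because change in GCS already requires it.

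**The case against.** **Fibrosis is not an irrelevant covariate.** Protocol 2.2 and 2.6.7 present late-enhancement fibrosis as closely tied to decline in left ventricular function, and both documents pre-specify the same model. This stands as a possible reason for including fibrosis. It does not explain leaving out baseline GCS, and the plan never gives it as the reason. That the wording was carried over remains an inference.

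**Boys without a contrast scan.** A reader might infer that the model does drop boys and rests on fewer of them than the ANCOVA. The documents do not show this. They do not say that GCS is read without contrast, or that any boy has GCS without a fibrosis score. Entry requires ability to undergo cardiac MRI, and Protocol 4.2 excludes a history of "hypersensitivity reaction to Gadolinium-based Contrast Agents (GBCA) required for MRI acquisition". Protocol 6.2.3.1 allows local laboratory tests to decide whether contrast is safe, so a missing score is possible but not demonstrated.

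**Precision.** A reader might infer that the odds ratio is less precisely estimated. That is the wrong way round. In logistic regression a prognostic covariate raises the standard error of the conditional log odds ratio: about 0.45 to 0.49 with baseline GCS against 0.44 with fibrosis, on assumed inputs. It also moves the estimate away from zero: simulated medians were 1.02 to 1.20 with baseline GCS against about 1.00 to 1.03 with fibrosis. Power rises on balance.

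**Regression to the mean.** This acts on both randomised arms alike and matters only through chance imbalance in baseline GCS.

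**Conclusion.** The point holds as a probable wording slip with a small cost. Baseline GCS is missing from the one model where the plan's own pattern calls for it, and this needs no assumption. The size does: about 1 to 7 points of power at N = 92, smallest at r = 0.9 and largest at r = 0.5, with every GCS input assumed. Type I error stays near 5%, so the comparison is valid. The responder odds ratio conditions on a different baseline from the ANCOVA beside it. Loss of subjects is conditional on boys who have GCS but no baseline fibrosis score.

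It would be tempting to say that the model gives up 15% to 25% of the outcome variance. That figure belongs to the continuous change score, whose ANCOVA already contains a baseline term, and it falls to 5% at r = 0.9. Nor do the documents contain data showing that baseline GCS drives the outcome; it is a component of it. The analysis is an additional look at an exploratory endpoint outside SAP Table 1, so no confirmatory conclusion is affected.

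**What to change.** In SAP 6.6.3.7, change the covariate of the responder model from baseline cardiac fibrosis score to baseline GCS, and add a line to SAP section 7 recording this as a change from Protocol 8.3.5. SAP section 7 already serves that purpose, so no protocol amendment is needed for this alone. If adjustment for fibrosis is intended, keep it alongside baseline GCS, give the reason, and state how a missing baseline fibrosis score is handled. The cost is a few words in the SAP and no new data, and the change is best made before unblinding.
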